7.2 Handling of Study Interventions

The study drug will be prepared and provided by the St Marys research pharmacy after randomization.

7.3 Concomitant Interventions

7.3.1 Allowed Interventions

All interventions necessary for the optimal medical therapy of the patients are allowed.

7.3.2 Required Interventions

None

7.3.3 Prohibited Interventions

Patients should not be on drugs that can significantly increase the risk side effects with bumetanide and furosemide, i.e., inotropic medications. New initiation of additional diuretic agents for synergistic diuresis (thiazide, acetazolamide, SGLT2 inhibitors and spironolactone) will be discouraged during the 24 hour study period to avoid electrolyte imbalance with potential randomization to very high dose diuretic arm. Following the 24 hour study period, addition of other diuretics and medications is as per the treating team per standard of care.

7.3.4 Adherence Assessment

The number of study drug administered and use of adjunct diuretics outside study protocol will be monitored and collected.

8. **STUDY PROCEDURES**

An overview of the scheduled evaluations is provided in the following table.

Schedule of Events

	Day of Consent (Day 1)	Day 2	Day 7⁴ (-4 days)	Day 90 (Phone visit) (+/- 30 days)
Informed Consent	X			
Physical Exam	X	X		
Randomization to Medical Therapy	X			
Administration of Medical Therapy	X ¹	X ¹		
Iohexol GFR testing	X ²	X ²		
Blood testing (NT proBNP, cystatin C, creatinine, hematocrit,)	X	X	X ⁷	
Research blood	X ³	X ³		
Urine testing (urine sodium, urine creatinine, NGAL, KIM-1)	X ³	X ³		
Electrocardiogram	X ⁵		X ⁶	
Echocardiogram	X	X		
Peripheral vein pressure	X	X		
Nocturnal Watchpat /Nox device screen	X	X		
Arterial Tonometry	X	X		
Ambulatory Blood Pressure	X	X		
Liver Elastography	X	X		
Adverse event assessment		X	X	X
Assessment for re-hospitalization				X
Concurrent medication assessment	X	X		X

¹Administration of Medical Therapy to be a total of 2 intravenous doses bid, administered by inpatient staff nurses

²Iohexol GFR testing (Renal Clearance) to be performed at bedside by CRTU staff

³Blood and urine samples to be collected by CRTU staff. Samples will either be collected by CRTU or transported by study staff to CRTU in tubes on ice when necessary.

⁴Day 7 or day of discharge, whichever is earlier

⁵Baseline ECG clinically indicated. If > 48 hours prior to randomization, must be repeated.

⁶ECG for research for comparison

⁷Estimated GFR at day 7 or discharge (whichever is sooner)

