3.3 Exploratory Objectives

- a) To compare length of hospital stay in the ultrahigh versus usual dose groups
- b) To compare total diuretic use in hospital between the ultrahigh versus usual dose groups
- c) To compare 90-day heart failure rehospitalizations between the ultrahigh versus usual dose groups
- d) To compare creatinine based GFR changes from baseline to day 7 or discharge (whichever is sooner) between ultrahigh versus usual dose groups
- e) To explore proteomic changes in blood and urine between the ultrahigh versus usual dose groups
- f) To examine changes in apnea-hypopnea index between ultrahigh and usual dose groups
- g) To determine daytime and nighttime blood pressure patterns between ultrahigh and usual dose groups
- h) To compare arterial stiffness alterations between ultrahigh and usual dose groups
- i) To explore changes in liver elastography in the ultrahigh versus usual dose groups

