7. Proteomic changes associated with high versus usual dose diuretics will be assessed to evaluate for differential expression of key pathways between the two strategies

4.4 .Significance:

1. The demonstration of safety and efficacy with ultra-high dose diuretic strategy compared to conventional diuretic infusion will be an important safety and preliminary efficacy finding to support a multicenter randomized phase III trial for superiority in relation to clinical outcomes.
2. Delineating mechanisms of hemodynamic benefit to more aggressive decongestion and relationship to renal indices will advance our understanding of human cardiorenal syndrome

4.5 Brief Synopsis of Methods:

- Accrual of 20 patients with decompensated heart failure requiring hospitalization randomized to ultra-high vs conventional dose diuretic arms in a double-blind design over 24 hours. Anticipate 25 patients will be enrolled to accrue 20 patients.
- Baseline assessment of renal lohexol clearance, echocardiography, blood sampling and urine sampling and nocturnal Watch Pat one assessment (apnea-hypopnea index), with all above assessments repeated after 24 hours.
- Follow up phone assessment at 90 days to assess heart failure readmission rates.

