5. STUDY DESIGN

This study is a double-blind randomized phase II pilot trial testing the safety and efficacy of ultra-high dose diuretics compared to standard dose diuretics over 24 hours in acute decompensated heart failure. Subjects will be screened after admission to the hospital with decompensated heart failure following stabilization and will be consented and offered participation in the trial. Once consent has been obtained, baseline serum and urine measures will be obtained along with administration of randomized treatment assignment for a total of 2 intravenous doses bid. An ambulatory blood pressure monitor (ABPM) will be worn for a 48 hour period starting from randomization. Additional mechanistic measures including short renal lohexol clearance (2 hour), echocardiography, arterial tonometry, liver elastography, and nocturnal apnea-hypopnea index (Watch Pat) will be performed. Final endpoint assessment with repeat of all baseline measures including lohexol clearance, echocardiography, arterial tonometry, liver elastography, and nocturnal apnea-hypopnea index (Watch Pat) will be performed on Day 2 after the 24-hour intervention. A final phone call visit at 90 days will assess for adverse events and heart failure hospitalization over the post discharge period.

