8.1.3 Follow-up Visits

Day 2 (24-48 hours)

All baseline testing including blood sampling and storage, urine sampling and storage, short Iohexol clearance, history/physical including weight, echocardiogram, arterial stiffness, liver scan, and nocturnal Watch Pat screen will be repeated 24 hours after initial assessment. ABPM will continue and terminate after 48 hours of blood pressure recording. Following this all study-related procedures will be complete. Hospital length of stay and total diuretic use will be documented. Clinical creatinine measurements obtained at Day 7 or discharge will be recorded for exploratory analyses. All AE's will only be collected for Days 1 through Day 7.

Day 90

Phone call to review hospitalizations, AEs, and concomitant medications. Re- Hospitalizations will be collected as AEs, not lab values. Following this all study-related procedures will be complete.

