9.5 Adverse Events and Serious Adverse Events

All patients will be evaluated for adverse events (AEs) and serious adverse events (SAEs) routinely at the time of follow-up evaluations. In addition, patients will be instructed to call in with concerns and/or present to their primary care providers. Should concerns for AEs and SAEs be raised, these will then be evaluated further. The time frame of evaluation for AEs and SAEs is confined to the duration of their participation in this study. All events are to be recorded within 1 day of the study team being notified regardless of their relationship to the study intervention and will be adjudicated and classified as outlined below.

For this study, and in agreement with general definitions, an AE is defined as

- Any unfavorable and unintended diagnosis, symptom, sign (including an abnormal laboratory finding), syndrome or disease which either occurs during the study, having been absent at baseline, or if present at baseline, appears to worsen.

A SAE is any adverse event that results in one or more of the following outcomes:

- Death
- A life-threatening event
- Inpatient hospitalization or prolongation of existing hospitalization
- A persistent or significant disability/incapacity
- A congenital anomaly or birth defect
- An important medical event based upon appropriate medical judgment

Date and Time of Onset

The date and time of onset is the date and time when the first sign(s) or symptom(s) were first noted. If the adverse event is an abnormal clinically significant laboratory test or outcome of an examination, the onset date is the date the sample was taken, or the examination was performed.

Classification of AE Severity

The Investigator must grade each adverse event according to the National Cancer Institute (NCI) Common Terminology Criteria for Adverse Events (CTCAE) (version 5.0). According to this guidance document all adverse events are rated on a 5-point scale corresponding to mild, moderate, severe, life-threatening, or disabling and death.

Each adverse event must be graded according to the specific criteria for grading as described in the CTCAE. For events not described in the CTCAE the following criteria will be used:

- Grade 1: Mild; asymptomatic or mild symptoms; clinical or diagnostic observations only; intervention not indicated.
- Grade 2: Moderate; minimal, local, or noninvasive intervention indicated; limiting age-appropriate instrumental ADL*.

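### The call that measures 90-day heart failure rehospitalisation may be made up to 30 days early, leaving part of the 90-day period unobserved (minor, exploratory outcome)

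*Combined protocol and SAP*

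**What the plan says.** All references are to the combined protocol and SAP.

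- **Outcome.** Section 3.3, item (c): "To compare 90-day heart failure rehospitalizations between the ultrahigh versus usual dose groups". It is one of nine exploratory objectives.
- **Timing.** In the Schedule of Events (Section 8), the row for assessing re-hospitalisation has one mark, in the column "Day 90 (Phone visit) (+/- 30 days"). Days are counted from "Day of Consent (Day 1").
- **Method.** Section 4.5 has "Follow up phone assessment at 90 days to assess heart failure readmission rates". Section 8.1.3 has "Phone call to review hospitalizations, AEs, and concomitant medications", then states that study procedures are complete.
- **Period covered.** Section 5: "A final phone call visit at 90 days will assess for adverse events and heart failure hospitalization over the post discharge period".
- **Recording.** Section 8.1.3 adds for rehospitalisations that "Hospitalizations will be collected as AEs, not lab values". For adverse events, Section 9.5 says: "The date and time of onset is the date and time when the first sign(s) or symptom(s) were first noted".
- **Analysis.** Section 11.5, items 1.3 to 1.6, does not list this outcome. The documents give no expected rate, counting rule, censoring rule or model for it.

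**The concern.** An outcome defined over a fixed 90 days needs each patient to be observed for 90 days, or an analysis that allows for shorter observation. The plan has neither. A patient called on day 60 is fully compliant with the schedule, yet nothing is learned about days 61 to 90. No second contact is scheduled and no chart review is planned for this outcome; the record extraction described in Section 12.2 names demographics, vital signs and examination findings. Patients called early can therefore only be undercounted.

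Late calls raise a lesser problem. A call on day 120 will also bring in admissions from days 91 to 120, and the plan does not say that these are left out.

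At stake is whether a figure labelled as a 90-day rate describes 90 days. Section 4.4 presents the pilot as support for a phase III trial on clinical outcomes. The documents do not say that this rate will be used to plan that trial, but the label should be accurate if it is quoted.

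**Working it through.** The plan states no figure for this outcome, so there is nothing of its own to reproduce. The steps below set out the window and illustrate its effect.

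**1. Window.** 90 − 30 = day 60; 90 + 30 = day 120. A call on day 60 leaves 90 − 60 = 30 days unobserved; a call on day 89 leaves one. The permitted spread in observation is 120/60 = 2.0.

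**2. Expected proportion found, by day of call.** Assumptions: constant hazard and true 90-day risk p. Formula: F(t) = 1 − (1 − p)^(t/90). For p = 25%, F(60) = 1 − 0.75^(2/3) = 17.5% and F(120) = 1 − 0.75^(4/3) = 31.9%.

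| Assumed 90-day risk | Call on day 60 | Call on day 120, no cut at day 90 |
|---|---|---|
| 15% | 10.3% | 19.5% |
| 25% | 17.5% | 31.9% |
| 35% | 25.0% | 43.7% |

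With a cut at day 90 the last column returns to the assumed risk. The day-60 column does not change, because the missing days were never observed. At p = 25% and 10 patients all called on day 60, the expected count is 1.75 instead of 2.5.

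**3. Average effect if calls are spread evenly over days 60 to 120 (p = 25%).** The hazard is h = −ln(0.75)/90, so 30h = 0.0959 and 60h = 0.1918.
- No cut: 1 − (0.8255 − 0.6814)/0.1918 = 24.9%. Early shortfall and late excess nearly cancel.
- Cut at day 90: the early half averages 1 − (0.8255 − 0.7500)/0.0959 = 21.3% and the late half 25%, so the mean is 23.1%. A cut without moving the window leaves a net undercount of about 1.9 points.

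**4. Effect on the between-arm comparison (p = 25%, 10 per arm, even spread, no cut).**
- SD of call day = 60/√12 = 17.3 days. SE of the between-arm difference in mean call day = 17.3 × √(2/10) = 7.7 days.
- Event density near day 90 = h × 0.75 = 0.24 percentage points per day.
- Typical shift from chance imbalance in timing = 7.7 × 0.24 = about 1.9 points.
- Sampling SE of the difference in proportions = √(2 × 0.25 × 0.75/10) = 19.4 points, about ten times larger.

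For scale, 3 events in 10 patients has an exact 95% interval of about 7% to 65%.

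**5. Origin of the 90 days.** The schedule counts from consent, in hospital; Section 5 speaks of the time after discharge. With an assumed 7-day stay, the window is 53 to 113 days after discharge; with 14 days, 46 to 106.

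**The case against.** The strongest reply is that the window governs when the call is made, not what the outcome is. The objective itself says 90 days, rehospitalisations are recorded as adverse events, and adverse events carry an onset date, so admissions after day 90 can be left out. For calls on or after day 90 this stands: what is missing is a written counting rule. Onset is the first sign or symptom, which need not be the admission date, so the rule should name the date it uses. For calls on days 60 to 89 the reply does not help.

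Second, Section 11.5, item 1.9, blinds patients and all study staff except pharmacy and the statistician, so call timing has no evident reason to differ by arm. This largely stands. Sections 10 and 11.1 allow unblinding after symptomatic hypotension or severe side effects, so blinding need not last to the call in every patient, but the documents point to no systematic difference.

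Third, Section 10 ends participation after 6 months, which might seem to permit later follow-up. It conflicts with Section 8.1.3 and schedules no contact, so it does not fill the gap.

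A reader might infer that the 90-day rate is not measured at all, or that the twofold window could produce a difference between arms of the order of 17.5% against 31.9%. The documents support neither. The first holds only for early calls. The second needs every patient in one arm to be called on day 60 and every patient in the other on day 120, with no cut.

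**Conclusion.** The point holds in a limited form and is minor. Calls on days 60 to 89 comply with the schedule but leave 1 to 30 days of the 90-day period unobserved, and the planned data cannot supply them. Calls on days 90 to 120 lose nothing, but need a written rule that excludes later admissions.

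The expected undercount for a patient called on day 60 is 7.5 points at an assumed 25% risk (17.5% instead of 25%), and smaller for calls nearer day 90. This rests on a constant hazard and on a risk that the documents do not give. The likely disturbance of the between-arm comparison is about a tenth of its sampling error if calls are spread evenly and timing does not depend on arm. The outcome is exploratory, has no specified analysis, and does not touch the primary endpoint. The reason to act is that the change is cheap and the missing days cannot be recovered from the planned data.

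**What to change.** 1. In the Schedule of Events, change the phone-visit window from ±30 days to 0 to +30 days.
2. In Section 8.1.3, have the call record the admission date of each heart failure hospitalisation.
3. In Section 3.3(c), or in Section 11.5 if the outcome is to be analysed, state that only admissions up to day 90 from one named origin are counted.
4. Choose that origin and reconcile the schedule's count from consent with the post-discharge wording in Section 5. If discharge is chosen, count the call's day 90 from discharge too; otherwise a call on day 90 from consent still falls short by the length of stay.
5. Reconcile the 6-month end of participation in Section 10 with Section 8.1.3.

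Items 1 and 3 belong together: working step 3 shows that the cut alone leaves an undercount. Censoring at the call date in a time-to-event analysis would also handle unequal follow-up without a schedule change, but would not observe the missing days.

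The cost is one table edit and a few sentences. There is no added visit or sample. The downside is that some calls are made up to a month later.

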8.1 Description of Evaluations

8.1.1 Screening Evaluation

Patients will be evaluated during their hospitalization for eligibility at St Marys hospital, Rochester, MN

8.1.2 Enrollment, Baseline, and/or Randomization

After confirming eligibility, informed consent will be obtained. Following consent, patients will be randomized 1:1 to ultrahigh vs standard dose diuretic strategies.

Day 1 (0-24 hours)

After randomization, patients will undergo comprehensive baseline assessment including weight, echocardiogram, history, and physical examination. Initial randomized therapy will be administered at least 6 hours after last clinically administered dose of IV diuretic (or immediately if no IV diuretic has been administered in the last 6 hours). Participants will be urged to void their bladders and discard urine at baseline immediately prior to receiving study drug. All baseline testing will be performed when feasible once consent is obtained. Baseline testing will include blood sample testing for NT proBNP, creatinine, cystatin C and hematocrit. Urine collection for urine creatinine and sodium will be specifically collected timed 1-2 hours after the administration of study diuretic dose to allow estimation of urine sodium excretion. 32 ml of blood and 30 ml of urine will be stored for future analyses. Peripheral venous pressure will be recorded from existing IV lines through pressure transducer monitoring from study team.

In addition to blood testing as above, Iohexol based GFR calculation using subcutaneously injected-Iohexol and timed samples of blood and urine to calculate GFR will be used for research with a procedure following typical inpatient practice Iohexol based GFR measurement. We will use the short Iohexol protocol with subcutaneous iothalamate injection (Time 0:T0), urine sampling at 1 hour after subcutaneous injection, with total urine volume collected over the 1-hour period (T0 to 1 hour). Urine and serum samples will be collected again approximately 45 minutes later from T60. Serum and urine samples for Iohexol will be collected at two time points after T0: i) T60 and ii) 45 minutes after T60. We will also continuously collect urine from subcutaneous injection until the end of the test, for quality control as per standard clinical practice. If Foley catheter is not present at baseline, participants will be asked to void voluntarily prior to renal study initiation with bladder scanning to confirm residual urine following bladder emptying. Ambulatory blood pressure monitoring (ABPM) will be recorded via an upper arm cuff on the non-dominant arm. Over a 48-hour period (Days 1 & 2), a blood pressure reading will be taken every 30 minutes during the day and every hour at night. Arterial stiffness will be assessed via carotid tonometry and placing a femoral and brachial blood pressure cuff on the upper thigh and upper arm. A liver ultrasound scan (Fibroscan) of the abdominal region will quantify liver elastography and potential liver disease.

Nocturnal screening for apnea-hypopnea index as a measure of sleep apnea will be performed using Watch Pat or Nox device. The Watch Pat is a non-invasive wrist monitor and will be worn overnight to test for sleep apnea. The Nox device is a portable polysomnography device to

measure sleep quality and determine sleep apnea presence. If patients have known sleep apnea, they will continue their home CPAP/BiPAP during the overnight test.

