In this pilot study we will therefore compare an ultra-high diuretic strategy with a conventional diuretic strategy in patients with decompensated heart failure with a primary efficacy end point of urine output at 24 hours. The primary safety endpoint will be a decline in serum creatinine estimated GFR by 50% of baseline value at 24 hours. This will be a double-blinded randomized pilot trial of ultra-high dose diuretics (IV bumetanide 12.5 mg bid for 24 hours vs IV furosemide at usual doses (twice the home dose of oral daily diuretic in furosemide equivalents administered bid). New initiation of adjunct diuretics (thiazide, SGLT2 inhibitors, acetazolamide, and spironolactone) will be discouraged during the 24-hour study period. Key secondary endpoints include weight change, NT-proBNP change, urine output, urine sodium excretion, creatinine, and cystatin C estimated GFR changes, apnea-hypopnea index, iohexol glomerular filtration rate, serum and urine proteomic analyses, peripheral vein pressure and echocardiographic changes over 24 hours, estimated GFR at day 7 or discharge (whichever is sooner) will each be compared by T test between the two groups.

4.2 Hypothesis:

Ultrahigh dose diuretic infusion will be associated with greater diuretic response and will not be associated with clinically significant decline in eGFR over 24 hours (defined as decline in creatinine estimated GFR of 50% from baseline at 24 hours).

4.3 Innovation:

1. Ultra-high dose diuretic strategies have not been compared to conventional diuretic strategies in a randomized trial
2. The use of a double-blind strategy will minimize bias in terms of diuretic adjustment and alternative therapies.
3. The measurement of serum and urine biomarkers of renal injury, peripheral vein pressure and echocardiography changes at baseline and at 24 hours will provide novel insight into the hemodynamic, renal, and cardiac response to decongestion.

4. The relationship between creatinine based GFR during non-steady state conditions such as active diuresis and extracellular volume reduction during diuresis, and true GFR measured by lohexol clearance testing has never been studied.
5. The effect of rapid diuresis on cardiac structure and function has not been well studied
6. The short-term effect of rapid volume removal on measures of sleep is unknown

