1.3 Primary and Secondary Outcomes

- 1.3.1 Primary outcome: urine output at 24 hours after initiation of intravenous diuretic.
- 1.3.2 Secondary outcomes: changes in the following measures over 24 hours after initiation of intravenous diuretic:
 - 1.3.2.1 Body weight
 - 1.3.2.2 NT-proBNP change
 - 1.3.2.3 Urine sodium excretion
 - 1.3.2.4 Apnea-hypopnea index
 - 1.3.2.5 Iohexol glomerular filtration rate
 - 1.3.2.6 Peripheral vein pressure
 - 1.3.2.7 Echocardiographic measures of cardiac output, estimated RV systolic pressure, RA pressure, LA strain, LV and RV global longitudinal strain, E/e'

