1.5 Secondary Analysis

- 1.5.1 Linear regression models will be used to estimate the between group difference in 24-hour change in each of the secondary outcomes; 95% confidence intervals will be constructed using t-based methods.

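### The SAP analyses urine sodium excretion as a 24-hour change, but no section defines a pre-dose sodium value to measure that change from

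*Combined protocol and SAP*

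**What the plan says.** **The analysis.** In Section 11.5.1, item 1.3.2 introduces the list with "Secondary outcomes: changes in the following measures over 24 hours after initiation of intravenous diuretic", and item 1.3.2.3 is "Urine sodium excretion". Item 1.5.1 adds: "Linear regression models will be used to estimate the between group difference in 24-hour change in each of the secondary outcomes". It names no baseline covariate.

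**The sampling.** Section 8.1.2 (Day 1) says: "Urine collection for urine creatinine and sodium will be specifically collected timed 1-2 hours after the administration of study diuretic dose". The purpose given is to estimate sodium excretion. Whether the first or the second study dose is meant is not stated. The same section says: "Participants will be urged to void their bladders and discard urine at baseline immediately prior to receiving study drug". The baseline laboratory tests it names are blood tests, and it also stores 30 ml of urine without a stated time.

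**Other mentions of Day 1 or baseline urine.**
- The Schedule of Events (Section 8) marks "Urine testing (urine sodium, urine creatinine, NGAL, KIM-1") for Day 1 and Day 2, with no clock time.
- Section 4.5 lists "echocardiography, blood sampling and urine sampling and nocturnal Watch Pat one assessment" at baseline, without naming sodium.
- Section 5 has baseline urine obtained together with the giving of randomized treatment, again without naming sodium.
- Section 4.3 concerns markers of renal injury: "The measurement of serum and urine biomarkers of renal injury, peripheral vein pressure and echocardiography changes at baseline and at 24 hours".
- Section 8.1.3 repeats urine sampling 24 hours after the initial assessment and gives no time from a dose.

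**The outcome as described elsewhere.** The Statistical Methodology row of Section 1 and the end of Section 4.1 attach the word change to weight and NT-proBNP but not to urine sodium excretion, and compare each endpoint by t-test. Section 11.4.2.1 lists the outcome in the same way.

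**The concern.** A change since initiation needs a value from before treatment acts. The plan times one Day 1 sodium sample, and that sample follows randomized treatment whichever dose is meant. If it serves as the reference, each arm's own early natriuresis is subtracted from its Day 2 value. Randomization does not protect such a contrast, because the reference is measured after the arms diverge. A larger sample would not cure it either, since the problem is what is being estimated and not its precision.

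Urine sodium excretion is called a key secondary endpoint and bears directly on the hypothesis of greater diuretic response (Section 4.2). The pilot is meant to support a phase III trial (Section 4.4). A null or reversed sodium result that came only from the choice of reference could mislead that decision.

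**Working it through.** **Step 1. Is there a plan figure to reproduce?** Not for sodium: the documents give no sodium effect, SD, correlation or power. The only power statement (Section 11.5.1, item 1.7.1) is for urine volume: 1688 ml, SD 1200 ml, 10 per group less 10% dropout, so 9 per group. The standardised effect is 1688/1200 = 1.407. A two-sided t-test at 0.05 with 16 df gives 79.99% power, against 80% stated. That figure stands and does not depend on the sodium question.

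**Step 2. Does any section supply a pre-dose sodium value?**

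| Section | Sodium named? | Time stated? | Stated to be before the first dose? |
|---|---|---|---|
| 8.1.2, timed collection | Yes | 1-2 h after a study dose | No, it is after a dose |
| 8.1.2, void before study drug | No | Immediately pre-dose | Yes, but discarded |
| 8.1.2, stored urine | No | No | No |
| Schedule of Events | Yes | Day only | No |
| 4.5, baseline urine sampling | No | Baseline, no clock time | No |
| 4.3, markers of renal injury | No | Baseline and 24 h | No |
| 5, baseline urine | No | With administration | No |
| 8.1.3, Day 2 repeat | No | 24 h after initial assessment | Not applicable |

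No row is both a sodium measurement and a stated pre-dose sample. No section says which sample is the reference for the change.

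**Step 3. What is estimated if the 1-2 h sample is the reference?** Let D1 be the true arm difference (ultra-high minus standard) in sodium excretion at the 1-2 h sample, and D2 the difference at the Day 2 sample.

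- Pre-dose reference: the expected arm difference at reference is 0 by randomization, so the change contrast is D2 - 0 = D2.
- 1-2 h reference: the change contrast is D2 - D1 = (k - 1) × D1, where k = D2/D1.
- Shortfall against D2: D2 - (D2 - D1) = D1, for every k.

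In units of D1:

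| k = D2/D1 | True Day 2 difference | Change contrast |
|---|---|---|
| 0 | 0 | -1 |
| 0.5 | 0.5 | -0.5 |
| 1 | 1 | 0 |
| 1.5 | 1.5 | +0.5 |
| 2 | 2 | +1 |

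The documents do not say which row applies. The rows for 0.5 and 1.5 are mirror images, so neither reversal nor the true direction can be presented as the expected result.

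**Step 4. Day 2 time from dose (assumption).** Suppose the timed sample follows the first dose and the Day 2 sample comes 24 h after it, at hour 25 to 26. If the second dose is given between hour 12 and hour 24, the Day 2 sample falls between 25 - 24 = 1 h and 26 - 12 = 14 h after the last study dose. The two samples may therefore also differ widely in time since dose.

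**The case against.** The strongest reply is that the valid analysis is already in the documents. Sections 1 and 4.1 treat sodium excretion as a quantity compared between groups by t-test, Section 11.4.2.1 reads the same way, and Section 8.1.2 collects the sample to estimate excretion, not a change. On this view the SAP list is simply loosely drafted: its NT-proBNP item repeats the word change under a stem that already says it. This stands in part. It shows an inconsistency between sections and points to the right repair. It does not remove the problem, because items 1.3.2.3 and 1.5.1 are the text an analyst would follow.

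A reader might go further and infer that the reference value certainly contains treatment effect. The documents do not support that. No section names the 1-2 h sample as the reference, and the untimed urine entries in Sections 4.5, 5, 8 and 8.1.2 leave room for a pre-dose sample. Discarding the last void does not exclude an earlier one. What is established is that the reference is undefined.

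A reader might also infer that sodium is the only secondary outcome whose baseline could follow treatment. That is not shown either. Section 8.1.2 does baseline testing when feasible after consent, and the Day 1 apnea-hypopnea recording is overnight, so it too may fall after the first dose.

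Finally, the trial is a 20-patient pilot, and the 1-2 h values are collected in any case. A level comparison remains possible and no data are lost. This stands and limits the severity.

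**Conclusion.** The point holds as a minor defect. The SAP specifies a change in urine sodium excretion without a defined pre-dose value, and this conflicts with Sections 1 and 4.1 and with the stated purpose of the timed sample in Section 8.1.2.

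The consequence is conditional. If the 1-2 h sample is the reference, the estimate targets D2 - D1: zero when the two differences are equal, opposite in sign to D1 when the later one is smaller, and always short of D2 by D1. This algebra needs no assumption beyond the choice of reference. The actual size and direction cannot be computed from the documents. Any probability of a misleading result would rest on assumed values of D1, D2/D1 and the within-patient correlation, so none is offered.

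The primary endpoint, its power statement and the safety endpoint are unaffected.

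**What to change.** 1. In Section 11.5.1, items 1.3.2.3 and 1.5.1, take urine sodium excretion out of the change list. Compare the timed 1-2 h post-dose value between arms as a level, and state which study dose it follows. A linear regression with group as the only term gives the same comparison as the equal-variance t-test, so this also agrees with Sections 1 and 4.1.
2. Report any Day 2 sodium value as a separate level, with its time from the last study dose.
3. Align the wording of Section 1 (Statistical Methodology), Section 4.1, Sections 8.1.2 and 8.1.3, Section 11.4.2.1, and items 1.3 and 1.5 of Section 11.5.1.
4. Optional: assay an aliquot of the pre-dose void that is now discarded and use it as a baseline covariate. If a true change from baseline is wanted, a pre-dose value of this kind is what it requires.

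Items 1 to 3 cost wording only, with no added visit, sample or patient. Item 4 costs one spot sodium assay per patient, on urine already voided and with an assay already run in real time (Section 12.2), and one degree of freedom in a 20-patient model.
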